During the abovementioned phase 1 trial of topical sodium nitrite, we observed no SAE's. We documented a grade 1 decrease in diastolic blood pressure below 50 mmHg, judged as possibly related to study drug 16 times in 4 participants. Of the four participants, two enrolled in Cohort 4, the highest concentration of the drug (2.0% sodium nitrite cream) and the other two enrolled into Cohort 3.a (1.8% sodium nitrite cream). The participants had fluctuating diastolic blood pressure measurements that occasionally reached below 50 mmHg even **before study cream application**; therefore, the association with study cream application is unclear. All events resolved spontaneously within an hour (i.e., at the next BP check).

15

PI: [name] Version 5

Experiments in rats showed that methemoglobin levels peaked at 45-50 min after application of 30 g/L sodium nitrite solutions on abraded skin³². Percutaneous absorption of a solution differs from the absorption rate from Aquaphor (the vehicle in our current preparation) and it seems to be slower than that from solution. There was no evidence of accumulation either, as predicted by our pharmacokinetic models^{34,35}.

In the proposed phase 2 trial we plan to answer this toxicity question, since we will be treating patients blindly with a placebo preparation and we will be able to ascertain whether the fluctuations in BP are intrinsic to this patient population, their frequent use of opioids, and/or chronic wide pulse pressure.

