3.0 Specific Aims

Hypotheses:

- •Topical sodium nitrite cream, at 2% concentration, is safe and well tolerated when applied for an extended period of time (10 weeks) in patients with sickle cell disease and leg ulcers.
- •Topical sodium nitrite accelerates healing of skin ulcers and decreases ulcer relatedpain compared to placebo in patients with sickle cell disease and leg ulcers.

Specific Aims:

- To determine the safety and tolerability of prolonged (10 weeks), twice a week application of topical sodium nitrite in patients with sickle cell disease and leg ulcers
- To determine if topical sodium nitrite accelerates wound healing as defined by >25% improvement over placebo arm
- •To determine if topical sodium nitrite decreases pain at the wound site >20% over placebo

Secondary Objectives:

- To evaluate the effect of hydroxyurea on leg ulcer's healing in combination with topical sodium nitrite or placebo
- To assess changes in ulcer microbiome after application of sodium nitriteor placebo and how they may relate to rate of healing
- •To evaluate the dermal composition and microvascular structure in the ulcer's biopsy of subjects enrolled on this study.

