PI: [name] Version 5 in order to assess cutaneous vascularization (i.e., angiogenesis), inflammation (tissue II-6, TGF- \Box , etc.), and markers of neurogenic inflammation³⁶.

At the end of 10 weeks of treatment, subjects that still have an open ulcer will be offered continuation of care at Montefiore or University of Pittsburg or referred back to the community.

Subjects will be followed off treatment but on study with monthly visits for an additional six months to evaluate the long term effect of topical sodium nitrite on the host and the ulcer (how many ulcers re-open or close). These visits will consist of measurement of all wounds by light photography and a detailed history of intervening ulcer treatments. If patients cannot return to the hospital or have moved away, we will call them and obtain the information on the phone and ask for a photograph. The photo can be obtained by the patient him or herself. Thereafter, they will be followed up with phone calls once a year for a total of 2 years, to establish whether this therapy is changing the natural history of ulcers in this population.

Rationale for the selection of subjects' number and endpoints

Sample size: We plan to randomize a total of 50 subjects to sample size of 20 completers per arm (40 subjects total) after an anticipated 20% dropout rate is taken into account. This sample size is determined based on feasibility of recruitment within the budget constraint and time frame of the study; we anticipate enrolling 1~2 eligible subjects per month. Although the focus of analysis will be more on estimation of treatment effect sizes and their 95% confidence intervals, the anticipated sample size is adequate to detect 88% vs. 48% response rate, as defined by >25% reduction of ulcer size from baseline, between treatment and control groups, with >80% at a two-sided significance level of 0.05 (see table 1). We note that in the Phase 1 study we observed an 88% response rate. Therefore, our study will be adequately powered if response rate in the placebo group is smaller than 48%.

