8.1 Primary Endpoints and Analysis

The primary endpoint of this phase II study will be the assessment of tolerability and occurrence of adverse effects of topical sodium nitrite compared to placebo.

- 8.1.1 Frequency of each adverse event will also be tabulated. To compare the safety of prolonged (10 weeks) treatments between the experimental/treatment and usual care/placebo groups, we will apply a non-parametric Mann-Whitney test on the number of adverse events.
- 8.1.2 Effect sizes of the treatment on the ulcer size reduction will be determined by differences in response rates or odds-ratios, and the 95% Cl's will accordingly be To test if topical sodium nitrite accelerates wound healing, as defined by >25% improvement over placebo arm, we will apply a Chi-square test. Logistic regression models will be applied if inclusion of confounding variables deems necessary. We will also test if declines of weeklymeasured absolute ulcer size on a continuous scale over the study period will be different between the two groups by applying mixed effects linear models for analysis of repeatedmeasure outcomes.
- 8.1.3 Effect sizes of the treatment on the pain reduction will be determined by differences in response rates or odds-ratios, and the 95% CI's will accordingly be estimated. To test if topical sodium nitrite decreases pain at the wound site >20% over placebo, we will apply a Chisquare test. Logistic regression models will be applied if inclusion of confounding variables deems necessary. We will also test if declines of weekly-measured absolute pain VAS scores on a continuous scale over the study period will be different between the two groups by applying mixed effects linear models for analysis of repeated-measure outcomes.

25

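### The primary safety endpoint gets a Mann-Whitney test on pooled adverse-event counts but no effect estimate or confidence interval, so a non-significant result would not exclude a relevant harm

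*Combined protocol and SAP*

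**What the plan says.** Section 8.1 makes safety relative to placebo primary: "The primary endpoint of this phase II study will be the assessment of tolerability and occurrence of adverse effects of topical sodium nitrite compared to" … The matching hypothesis in section 3.0 is that the 2% cream "is safe and well tolerated when applied for an extended period of time (10 weeks) in patients with sickle cell disease and leg ulcers".

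Section 8.1.1 plans two things. One is descriptive: "Frequency of each adverse event will also be tabulated". The other is the comparison between arms: "we will apply a non-parametric Mann-Whitney test on the number of adverse events". It names no effect measure, interval or criterion for the safety conclusion.

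Elsewhere the plan leans towards estimation. The sample-size text in section 5.2 says that "the focus of analysis will be more on estimation of treatment effect sizes and their 95% confidence intervals". Section 8.1.3 carries this through by planning interval estimates for pain: "Effect sizes of the treatment on the pain reduction will be determined by differences in response rates or odds-ratios, and the 95% CI's will accordingly" … Section 8.1.2 has parallel wording for ulcer size, though its sentence breaks off in the text available.

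The only power statement, "with >80% at a two-sided significance level of 0.05", concerns ulcer response of 88% against 48%. Section 5.2 says that feasibility set the sample size.

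**The concern.** That a cream is safe is close to a claim of no important difference. A two-sided difference test without an interval can show harm, but it cannot show how much harm has been ruled out. If the test is not significant, the reader of the final report learns neither the size of the observed excess nor the largest excess compatible with the data. The efficacy aims are to get that information; the primary endpoint is not.

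The count also pools everything. Table 3 in section 12 lists dozens of events expected from sickle cell disease itself. They enter the same total as the few events in Table 2 that the cream might cause, so a cream-specific harm is diluted.

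The protocol presents this trial as the step from phase I towards phase III. An upper bound on excess harm is what that decision needs from the primary endpoint.

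**Working it through.** **1. The plan's own power figure.** Inputs from section 5.2: 20 completers per arm, 88% against 48%, two-sided 0.05. The mean proportion is 0.68.

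- Standard error under no difference: √(2 × 0.68 × 0.32 / 20) = 0.1475.
- Standard error under the alternative: √((0.88 × 0.12 + 0.48 × 0.52) / 20) = 0.1333.
- Power = Φ((0.40 − 1.96 × 0.1475) / 0.1333) = Φ(0.83) = 79.7%.

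Exact enumeration of the uncorrected chi-square test gives 82.1%. The stated figure is reproduced, but it describes ulcer response and says nothing about safety.

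**2. Power of the Mann-Whitney test on counts.** The arm sizes are 25 randomised (50 in total, 1:1) and 20 completing. The documents give no placebo adverse-event rate or dispersion, so these are assumptions: negative binomial counts, placebo mean 2 to 4, size 1 or 2. The test is two-sided at 0.05, tie-corrected, with 20,000 simulated trials per setting.

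| Per arm | Size | Mean | Rate × 1.5 | Rate × 2 |
|---|---|---|---|---|
| 20 | 1 | 2 | 15.4% | 35.0% |
| 20 | 1 | 4 | 16.3% | 39.3% |
| 20 | 2 | 2 | 22.9% | 55.8% |
| 20 | 2 | 4 | 27.1% | 65.7% |
| 25 | 1 | 2 | 17.4% | 42.5% |
| 25 | 1 | 4 | 19.7% | 47.3% |
| 25 | 2 | 2 | 26.9% | 66.1% |
| 25 | 2 | 4 | 33.3% | 75.2% |

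The ranges are about 15–33% and 35–75%. A separate run of the same settings gave 16–32% and 34–75%, the same to within simulation error. With no true difference the rejection rate was 4.7–5.2%.

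**3. Dilution.** Section 2.4 reports low diastolic pressure in 4 of 18 phase 1 subjects (22%). Suppose the cream adds one event in 22% of active subjects, on the same background counts. The pooled test then has about 6–7% power, little above its 5% error rate. Analysed as its own event, 22% against an assumed 4%, Fisher's test has 25% power (20 per arm) or 30% (25 per arm).

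The result depends heavily on the scenario. All four cases were in the two strongest phase 1 cohorts, which had 4 and 3 subjects, and they had 16 events between them. If 4/7 of active subjects each had four extra events, power would be 46–88%.

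**4. When no events are seen.** The one-sided 95% upper bound p solves (1 − p)ⁿ = 0.05.

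- n = 25: 1 − 0.05^(1/25) = 11.3%.
- n = 20: 1 − 0.05^(1/20) = 13.9%.

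**5. What an interval would show.** Assume 20% against 5% of subjects affected. The approximate 95% half-width is 1.96 × √((0.20 × 0.80 + 0.05 × 0.95) / n), which is 17.9 points at n = 25 and 20.0 points at n = 20. That is wide, but it can be reported.

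**6. Why a formal margin is not the remedy.** Assume 20% in both arms, one-sided 0.025 and 80% power. Then n = 2 × 0.20 × 0.80 × (1.96 + 0.84)² / margin². A 20-point margin needs about 63 per arm and a 15-point margin about 112.

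**The case against.** A fair defence has four parts.

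- **The test does not stand alone.** Section 8.1.1 tabulates each event, which partly answers the dilution argument. There are also blood-pressure and methemoglobin monitoring, relatedness criteria, stopping rules (section 7.2) and a DSMB (section 13). This stands, so the gap is in inference between arms and not in safety oversight. A frequency table carries no statement of uncertainty, and stopping rules do not say what excess the final data exclude.
- **Section 5.2 already promises intervals.** Its sentence is not restricted to efficacy. That is true, but it names no safety quantity, and section 8.1.1, where one belongs, has none.
- **Text may be lost.** Section 8.1.2 visibly drops words, and section 8.1.1 opens with an *also* that refers back to nothing. A missing safety sentence cannot be ruled out, though nothing shows that there was one.
- **This is a small, feasibility-sized phase II trial.** That argues for estimates with bounds over a test.

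A reader might go further and infer that a relevant harm would be missed in some 60–80% of trials and then reported as safe. The documents do not support this. They give no background rate, dispersion or threshold for a relevant harm. Across plausible assumptions the chance of a miss runs from near zero (Poisson counts, mean 5, doubled rate) to over 90%. No section says that non-significance will be read as safety. On blood pressure, section 2.4.2 says that "we will be able to ascertain whether the fluctuations in BP are intrinsic to this patient population"; that poses an open question and commits the plan to no particular answer.

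**Conclusion.** The point holds as a gap in specification. For the primary endpoint, the only planned inference between arms is a significance test on pooled counts, with no effect estimate, interval or power. At 20 to 25 per arm, non-significance would leave relevant harms open. Two results carry this:

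- The zero-event bounds of 11.3% and 13.9% follow from the sample size alone.
- The power ranges of about 15–33% (50% higher rate) and 35–75% (doubled rate) rest on assumed negative binomial counts with mean 2 to 4 and size 1 to 2. They illustrate the problem and are not properties of the plan.

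The plan states no rule that would turn a non-significant test into a claim of safety. It also does not say what result would support the hypothesis, which is why the reading should be fixed in advance. The change is worth making because it is cheap and brings the primary endpoint up to the standard the plan sets for pain.

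**What to change.** In section 8.1.1:

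- Report the active-to-placebo ratio or difference of adverse-event rates with its 95% confidence interval.
- For each event in Table 2, report the difference in the proportion of subjects affected with an exact or score 95% interval. Where no events occur, give the upper confidence bound.
- Base the safety conclusion on the largest excess that these bounds exclude.
- State that a non-significant Mann-Whitney result is not evidence of safety, and keep that test as descriptive.

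In the sample-size text of section 5.2, say that the power above 80% refers to ulcer response only. Do not add a safety power figure, since it would rest on event rates that the documents do not supply.

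The cost is a few sentences and a few more lines of output, with no new data or patients. The downside is that the bounds will be wide, so the safety statement will read less favourably.

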> experienced a decrease in leg ulcer surface area, fig 1 (pretreatment 4.65 vs. post-treatment 2.78 cm^2 , p < 0.001), and improvement in pain scores at the ulcer site (pretreatment VAS score of 4.87 vs. post treatment of 2.91, p=0.024). Changes in pain score were not statistically significant at the ulcers that were not treated with study cream, p=0.96 (50% of subjects had more than one ulcer and only one was treated with study cream). Healing was dependent on sodium nitrite concentration, and it was most marked in cohort 4 (2.0%), the one treated with the highest strength of sodium nitrite cream, with 2 of 3 subjects experiencing complete closure of the ulcer (89% decrease in surface area), then cohort 3a (1.8%), with a 68.5% healing rate and

[figure not shown]

Figure 1: Changes in leg ulcer surface area before and after application of sodium nitrite cream (A) Wound size measured by digital planimetry. (B) Wound sizes measured manually (longest length and widest width). (C) Changes in wound size according to sodium nitrite concentration. Arrows in (A) and (B) represent first application of cream. Plotted points or bars are mean values and error bars are standard error of the mean. *p=0.0058 compared with first application. †p<0.0001. ‡p=0.0001. §p=0.0008. from Lancet Haematology 1, e95-e103. PMC4415859 (Figure 1, PI is first author)

one out of 4 experiencing complete closure, then cohorts 1, 2 and 3 with healing rates of 29, 3.8 and 33%, respectively. See Table 1 below.

11

PI: [name] Version 5

Table 1 : Percent of ulcer's surface healed from beginning of therapy								
Cohort/concentration	Week 3	End of study						
1/0.5%	29.9%	28.8%						
2/1.0%	15.8%	3.8% (one subject progressed)						
3/1.5 %	22.5%	32.9%						
3a/1.8%	56.0%	68.5% (one of four ulcers closed completely)						
4/2.0%	55.1%	88.6% (two of three ulcers closed completely)						

Application of topical sodium nitrite was associated with a significant increase in periwound cutaneous blood flow measured by laser speckle contrast imaging and increased periwound skin temperature by infrared thermography (fig 3).

[figure not shown]

Figure 2 legend: Top panels: Laser speckle analysis of blood flow before (A) and after (B) application of sodium nitrite

 $\textbf{Lower panels: } Infrared \ photography \ of \ an \ individual \ subject \ before \ application \ (C) \ of \ topical \ baseline) \ and \ immediately \ after \ (D).$

[figure not shown]

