- Apply 2 layer compression wrap to leg (depending on the condition of theulcer)
- Use of topical or systemic antimicrobials

All participants will be requested to complete the Brief Pain Inventory (BPI) prior to initiation of the therapeutic portion of the trial.

Baseline visit: The following tests will be performed:

- 1. Baseline labs, which include CBC, reticulocyte count, CRP, ESR, LDH, hepatic panel, basic metabolic panel, ferritin, Pro-B Natriuretic Peptide (BNP), urinalysis, urine microalbumin, uric acid, urine pregnancy test (female at reproductive age)
- 2. Research labs: Pax gene, and stored 5-10 cc blood samples
- 3. Saliva for DNA analysis
- 4. The surface area of ulcer(s) will be measured and photographed with defined lighting, distance, exposure and camera type
- 5. A pain assessment tool (VAS assessment)
- 6. Brief Pain Inventory (BPI), ASCQ-ME, PROMIS surveys, Beck Depression Inventory

Screening visit and baseline visits can be combined in one appointment.

After at least two weeks of "run in period", where the patient is treated with standard of care therapies only, the total ulcer surface will be measured and, if there isn't a reduction of>25%, the patient will be randomized to receive sodium nitrite cream or placebo.

A biopsy of the ulcer will be obtained in patients that consent during the run inperiod.

Week 1/Visit 3: First application of "study cream". After cleaning the wound, the wound will be measured by light photography and manually by wound nurse, a microbiome sample will be obtained, and the "study cream" will be applied to all the ulcerated surfaces. Vital signs will be obtained before application to establish baseline MAP and post-application at hours 1, 2, 3, 4, 5. If no significant decrease in MAP pressure from baseline is detected (clinically significant hypotension, or symptomatic dizziness, tachycardia, or hypoxia as per the judgment of the PI), the patient will be discharged and instructed to return for a second application two to three days later. Methemoglobin will be obtained one hour ± 30 min after creamapplication.

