7.2 Stopping Rules

The study medication will be stopped if the subject experiences healing of the ulcer.

Subjects will be removed from therapy should one or more of the following occur:

- If any methemoglobin reading is >7.5%, the research study cream will be discontinued.
- Investigator or patient considers discontinuation of the study to be in the patient's best interest.
- Clinically significant hypotension (decrease in the systolic BP >20mmHg from the baseline systolic BP and of 10mmHg from the baseline diastolic BP application, and symptomatic dizziness, tachycardia, or hypoxia as per the judgment of the PI).
 - A dose will be skipped if the subject has a systolic blood pressure of ≤80mmHg and/or a diastolic blood pressure of ≤50mmHg, once the blood pressure has been checked with a repeat blood pressure check. If three doses are skipped in a row for this reason, the subject will be removed from therapy.
- Sustained pulse oxygen saturation below 85% for >15 minutes while on supplemental oxygen (up to 4L by NC).

- Increased ulcer pain requiring increased opioid use by 50%.
- Development of osteomyelitis or other systemic infection while on therapy.
- Lack of compliance, as measured by missing more than two sequential cream applications and/or at the PI's discretion.

Rules for Stopping the Study:

- Occurrence of severe toxicities:
 - Three subjects requiring sodium nitrite cream discontinuation
 - Death while on protocol, if it is attributable to the sodium nitrite cream

8. **Analysis of the Study**

We will first review and summarize data using descriptive summaries and graphical analyses to ensure recorded values are within appropriate ranges, in order to check for outliers and abnormal values. We will explore the success of randomization by comparing groups on potential confounding variables, and will include variables that are not equally distributed between groups in multivariable models. For primary analyses, we will adhere to the intent-totreat analysis principle that assigns groups as randomized as opposed to actually treated. For sensitivity analyses, we will conduct as-treated analysis and use incomplete data as well after imputation of missing data due to early dropouts; imputation methods such as last-observationcarried-forward or MCMC will be conducted and results from thereof will be compared.

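### The supportive weekly models for pain and ulcer size do not prespecify how the pre-treatment value enters, so precision may be lost and the model choice depends on the data

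*Combined protocol and SAP*

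**What the plan says.** Sections 8.1.2 and 8.1.3 each have two layers. The first is a chi-square test of responder rates, with logistic regression if confounders call for it; effect sizes and their 95% CIs are response-rate differences or odds ratios. The second is a mixed effects linear model on the weekly values. For pain: "We will also test if declines of weekly-measured absolute pain VAS scores on a continuous scale over the study period will be different" between the groups. The ulcer-size sentence is parallel. Neither names a covariate, a covariance structure or the role of the pre-treatment value.

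The only general covariate rule is in the opening paragraph of Section 8: after comparing the groups, the analysts "will include variables that are not equally distributed between groups in multivariable models". It gives no threshold for imbalance.

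The pre-treatment values exist. Section 5.3 lists ulcer area and "A pain assessment tool (VAS assessment)" at the baseline visit. Section 5.2 has ulcers measured again after the run-in, with pain assessed each time size is measured. Randomization comes after the run-in and before the first cream.

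Section 5.2 plans a "sample size of 20 completers per arm (40 subjects total)" "after an anticipated 20% dropout rate is taken into account". It states power only for ulcer response: "the anticipated sample size is adequate to detect 88% vs. 48% response rate", "with >80% at a two-sided significance level of 0.05".

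**The concern.** In a model with arm, time and arm-by-time terms, each arm's starting level is estimated separately. Randomization makes the true starting means equal, so that separate estimate only adds noise: chance differences in starting pain, and the regression to the mean that follows, enter the estimated difference in decline. Fixing a common starting mean, or conditioning on the starting value, removes the part of that noise which baseline predicts.

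The imbalance rule in Section 8 does not do this job. The precision gain comes from baseline predicting outcome, and it is there when the arms look balanced, which is when the rule would leave baseline out. The rule also means that the model, and so the reported estimate, is settled after looking at the data.

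Pain and ulcer healing are both specific aims, and the plan wants effect sizes for planning phase III. What is at stake is the precision and prespecification of the continuous-scale estimates.

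**Working it through.** **The plan's own figure.** For 88% vs 48%, 20 per arm, two-sided 0.05, pooled normal formula: z = [0.40·√20 − 1.96·√(2·0.68·0.32)] / √(0.88·0.12 + 0.48·0.52) = (1.789 − 1.293)/0.596 = 0.83, so power is 79.7%. Exact power of the uncorrected chi-square is 82.1%. The stated figure is reproduced, and 40/0.8 = 50 randomized agrees. It concerns ulcer response only; no power is stated for pain or for either weekly model.

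**Inputs for pain**
- 20 per arm, two-sided 0.05 (Section 5.2).
- A 2-point mean difference, for illustration. Section 5.2 gives 2 points on the 0-10 VAS as a threshold for meaningful change, not as a powered between-arm effect.
- SD of change. Section 2.4 reports "improvement in pain scores at the ulcer site (pretreatment VAS score of 4.87 vs. post treatment of 2.91, p=0.024)", a fall of 1.96. Assuming a paired t-test with n = 18, t(17) = 2.478 and SD = 1.96·√18/2.478 = 3.36. The test is not named.
- Correlation ρ between the starting and final values: not given; assumed 0.5, with 0.3 and 0.7 as the range.
- Eleven weekly values, weeks 0-10, with equal variance at the start and the end.

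**Compound symmetry, by hand.** Σ(t − mean)² = 110, Σt² = 385, (Σt)² = 3025.
- Separate starting means: SE of the 10-week difference = 10·√(2/20)·√[(3.356²/2)/110] = 0.715.
- Common starting mean: 110 is replaced by 385 − 3025·ρ/(1 + 10ρ). At ρ = 0.5 this is 132.9, and SE = 0.715·√(110/132.9) = 0.651.
- The interval is narrower by 1 − √(110/132.9) = 9.0%. At ρ = 0.3 the term is 158.1 (16.6%); at ρ = 0.7 it is 120.3 (4.4%). The SD cancels.

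**Start and end values only.** Unadjusted SE = 3.356·√(2/20) = 1.061. The ratio of ANCOVA SE to change-score SE is √((1 + ρ)/2): 0.866 at 0.5, 0.806 at 0.3, 0.922 at 0.7. The autoregressive weekly model behaves almost the same way (1.061 vs 0.918 at ρ = 0.5).

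**Power (noncentral t, 38 df), separate vs common starting mean, SD of change 3.36**

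| Structure | ρ = 0.3 | ρ = 0.5 | ρ = 0.7 |
|---|---|---|---|
| Compound symmetry | 77.8% vs 90.4% | 77.8% vs 85.0% | 77.8% vs 81.3% |
| Autoregressive | 45.2% vs 63.1% | 45.1% vs 56.5% | 45.1% vs 51.3% |
| Random slope, residual share 0.2 | 51.6% vs 69.3% | 54.7% vs 65.6% | 63.4% vs 68.5% |
| Random slope, residual share 0.4 | 60.0% vs 77.3% | 68.7% vs 77.8% | not attainable |

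The gains are about 7-11 points at ρ = 0.5, 13-18 at 0.3 and 4-6 at 0.7. The interval narrows by about 9-14%, 17-20% and 4-8% respectively.

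**Smaller SD.** The Precis attaches p<0.0001 to the phase 1 fall in ulcer pain. Under the same paired-t assumption, t(17) is at least 5.04 and SD is at most 1.96·√18/5.04 = 1.65. At ρ = 0.5, power is then 96.2% vs 99.1% (change score vs ANCOVA, and also autoregressive) and about 100% either way under compound symmetry: a gain of 0-3 points.

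**Variance growing over time.** The random-slope rows hold start and end variance equal. If slopes vary independently of starting level (slope SD 0.15-0.30 per week, VAS SD 2.5-3.35 and correlation 0.5 before the slopes are added), the gain is 1.6 points (45.1% to 46.7%) to 5.6 points (64.5% to 70.1%). The SEs are 1.088 vs 1.065 and 0.857 vs 0.804, so the interval narrows by only about 2-6%.

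**The case against.** The strongest reply has five parts.

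- **These models are supportive.** The primary endpoint is tolerability and adverse effects, and sample size rests on feasibility. The effect sizes and 95% CIs that the plan stresses come from response rates or odds ratios, and ulcer response is already defined relative to baseline. This stands. A reader might infer that the plan's main intervals are needlessly wide; Section 8.1 does not support that.
- **No single power loss can be claimed.** The SD of 3.36 comes from an unnamed test, and the Precis p-value points to a much smaller SD, though it may belong to a different, dose-related model. The top of the correlation range is also strained: ρ = 0.7 with SD of change 3.36 implies a VAS SD of 3.356/√0.6 = 4.33, against a maximum of √(2.91·7.09) = 4.54 on a 0-10 scale with mean 2.91. This stands. Reading 7-11 points as a known cost of the plan goes beyond the documents.
- **The 2-point effect is borrowed** from a change threshold. This stands; it is used only as an illustration.
- **The plan does not exclude adjustment.** Section 8 allows it after imbalance, and the weekly models are unspecified rather than specified without baseline. The wording point stands, so a reader should not infer that the plan forbids adjustment. But a rule triggered by observed imbalance neither secures the precision nor fixes the model in advance.
- **A subject random intercept already absorbs stable differences in starting pain.** True in part: the compound-symmetry row includes one, and a gain remains there unless ρ is high or the SD small.

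**Conclusion.** The point holds as a gap in prespecification with a conditional precision cost. Neither weekly model says how the pre-treatment value enters, and the one general rule makes that depend on observed imbalance.

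For pain, with 20 per arm, a 2-point difference, SD of change 3.36 and equal variance over time, proper handling of baseline adds about 7-11 points of power at ρ = 0.5, 13-18 at 0.3 and 4-6 at 0.7. It adds about 0-3 at ρ = 0.5 if the SD of change is nearer 1.65, and less than the main figures if variance grows over time. Across everything computed, the gain runs from about 0 to 18 points, and adjustment lowered power in none of the cases. Under equal variance, the interval for the arm difference narrows by about 9-14% at ρ = 0.5 whatever the SD.

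The responder-rate and odds-ratio intervals do not change. A reader might carry the pain figures over to ulcer size, but the documents give no SD for ulcer area, so no figure can be derived there; the prespecification gap is the same. The change should be made, but the trial's stated power does not turn on it.

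**What to change.** In Sections 8.1.2 and 8.1.3, name the last value before the first cream application as baseline and state that it enters the weekly model whatever imbalance is seen. Either of two forms will do:

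1. Keep baseline among the responses and constrain the arms to a common mean there (time and arm-by-time terms, no arm term at time 0).
2. Enter baseline as a covariate, with post-baseline values only as the outcome.

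Report the adjusted arm difference at end of treatment with its 95% CI. State the covariance structure and include the hydroxyurea stratum. If a power gain is quoted, give it as a range with its SD and correlation assumptions.

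The cost is wording in the analysis section. No new data are needed, and at most one model degree of freedom is spent.
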